Appendix A- Eligibility Checklist

| | | |
|--------------------------------------------------------------------------------------------------------------------------------------------------------------------------------------------------------|--------------------|--|
| IRB Protocol No. 00055981 | SUBJECT ID: | |
| Study Title: SINGLE INJECTION INTERSCALENE BRACHIAL PLEXUS NERVE BLOCK WITH ADJUVANTS VS. LIPOSOMAL BUPIVACAINE INTERSCALENE BRACHIAL PLEXUS NERVE BLOCK FOR TOTAL SHOULDER ARTHROPLASTY | | |
| Principal Investigator: [name], D.O. | | |

| Inclusion Criteria (as outlined in study protocol) | Criteria is met | Criteria is NOT met | Source Used to Confirm * (Please document dates and lab results) |
|------------------------------------------------------------------------------------------------------------------------------|-------------------------------------|--------------------------------|-----------------------------------------------------------------------------------|
| All patients who are undergoing total shoulder arthroplasty |  |  | |
| Age >18 years |  |  | |
| Ability to understand and willingness to sign IRB-approved informed consent document |  |  | |
| Weight Greater than or equal to 50 kg |  |  | |
| ASA patient status I-III |  |  | |
| Exclusion Criteria (as outlined in study protocol) | Criteria NOT present | Criteria is present | Source Used to Confirm * (Please document dates and lab results) |
| No contraindications to an interscalene block or phrenic blockade. |  |  | |
| Infection at injection site. |  |  | |
| Pre-existing neurological dysfunction affecting the operative extremity. |  |  | |
| Patients who abuse narcotics or have chronic pain (using greater than 40 mg equivalents of oxycodone per day) |  |  | |
| Patients who are wards of the state |  |  | |
| BMI >40 |  |  | |
| Uncontrolled diabetes (HbA1c >8.0) |  |  | |
| Contraindications to any pain-control agents planned for surgical or postsurgical use (ie, bupivacaine, hydromorphone, etc.) |  |  | |

Single Injection interscalene brachial plexus nerve block with adjuvants vs. Liposomal bupivacaine
interscalene brachial plexus nerve block for total shoulder arthroplasty

| | | | |
|---------------------------------------------------------------------------------------------------------------------------------------------------------------------------------------------------------|--------------------------|--------------------------|--|
| History of allergic reactions attributed to compounds of similar chemical or biologic composition to bupivacaine or liposomal bupivacaine or its adjuncts (dexamethasone, buprenorphine, or clonidine). |  |  | |
| Patients with moderate-severe hepatic or renal impairment. |  |  | |
| Patient is pregnant or lactating |  |  | |
| Patient has a labeled contraindication for the study drug, such as a systemic fungal infection |  |  | |
| Patients undergoing repeat shoulder arthroplasty or reverse total shoulder arthroplasty. |  |  | |

This subject is eligible / ineligible for participation in this study.

REDCap Assigned PID: _____

Signature of research professional confirming eligibility: _____

Date: ____ / ____ / ____

Signature of Treating Physician: _____

Date: ____ / ____ / ____

Signature of Principal Investigator**: _____

Date: ____ / ____ / ____

* Examples of source documents include clinic note, pathology report, laboratory results, physical exam, etc. When listing the source, specifically state which document in the medical record was used to assess eligibility. Also include the date on the document. Example: Pathology report, 01/01/14" or "Clinic note, 01/01/14"

**Principal Investigator signature can be obtained following registration if needed

Single Injection interscalene brachial plexus nerve block with adjuvants vs. Liposomal bupivacaine
interscalene brachial plexus nerve block for total shoulder arthroplasty

Appendix B – Protocol Registration Form

DEMOGRAPHICS

Patient: Last Name: _____ First Name: _____

MRN: _____ DOB (mm/dd/yy): ____ / ____ / ____

ZIPCODE: _____

SEX: Male Female Ethnicity (choose one): Hispanic
 Non-Hispanic

Race (choose all that apply): WHITE BLACK ASIAN

PACIFIC ISLANDER NATIVE AMERICAN

Height: _____.____ inches Weight: _____.____ lbs. (actual)

Surface Area: _____.____ m²

Primary Diagnosis: _____

PROTOCOL INFORMATION

Date of Registration: _____ / _____ / _____

MD Name (last) : _____

Date protocol treatment started: _____ / _____ / _____

Informed written consent: YES NO

(consent must be signed prior to
registration)

Date Consent Signed: _____ / _____ / _____

PID # (to be assigned by REDCap): _____

Single Injection interscalene brachial plexus nerve block with adjuvants vs. Liposomal bupivacaine
interscalene brachial plexus nerve block for total shoulder arthroplasty

Appendix C – Pain Assessment Form

Subject Number: _____ DATE: ____/____/____ TIME: ____:____ AM/PM

1 - Rate the intensity of your worst pain in the past 12 hours related to your operated shoulder

0 1 2 3 4 5 6 7 8 9 10

2 - Did you take prescription pain pills in the past 24 hours? YES NO

If yes please circle the medication below

2a1 – Oxycodone (Roxicodone)

2a2 - Hydromorphone (Dilaudid)

2a3 - Hydrocodone + acetaminophen (Vicodin, Norco)

[figure not shown]
2a4- Oxycodone + acetaminophen (Percocet)

2a5 -Diazepam (Valium)

2a6- Alprazolam (Xanax)

Single Injection interscalene brachial plexus nerve block with adjuvants vs. Liposomal bupivacaine interscalene brachial plexus nerve block for total shoulder arthroplasty

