4.0 Study Outcomes and Study Measures

4.1 Primary Outcome

- 4.1.1 The primary outcome of this study is the area-under-the-curve (AUC) of the mean visual analog scores numerical rating system (VAS-NRS) within the first 48 hours postoperatively. Pain levels (with shoulder movement) will be measured upon arrival to the PACU, at 6 hours, 12 hours, 24 hours, 36 hours, and 48 hours after surgery.
 - 4.1.1.1 The mean AUC48 of the liposomal bupivacaine ISB group was 136.4 with a standard error of 12.09.¹⁰
 - 4.1.1.2 There are no existing data to predict the mean AUC48 for ISB using plain bupivacaine +adjuvants, but we predict that this value will be within 20% of the mean AUC48 of the liposomal bupivacaine group, for a value of ~163.0.

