5.0 Treatment Plan

Table 1- Protocol stages

| | Day of Surgery- Pre-op | Intraoperative | 15 departure from PACU | 6 hours postop | 12 hours postop | 24 hours postop | 36 hours postop | 48 hours postop |
|------------------------------------------------------------------------------------|---------------------------|----------------|---------------------------------|----------------------|-----------------------|-----------------------|-----------------------|-----------------------|
| Pre-operative pain score | X | | | | | | | |
| Preoperative multimodal regimen unless contraindicated | X | | | | | | | |
| Receive ISB with Exparel or plain bupivacaine + adjuvants | X | | | | | | | |
| Receive short-acting IV opioids if needed | | X | | | | | | |
| Rescue opioids if needed | | | X | X | X | X | X | X |
| Postoperative multimodal regimen | | | | X | X | X | X | X |
| Pain score assessment in diary | | | X | X | X | X | X | X |
| Patent diary of narcotic use | | | X | X | X | X | X | X |
| Study coordinator contact via phone call | | | | | | X | | X |
| Patient satisfaction assessed via Likert scale. Review of potential adverse events | | | | | | | | X |

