5.1 Study-Related Activities

Patients will be recruited from 2 sites- Wake Forest Baptist Health (Main Campus) and WFBH Davie. Patient involvement in the study will be initiated upon scheduling of their surgery with the Anesthesiology team. Eligible subjects will be identified via eligibility checklist (Appendix A) and contacted via phone call to inform them of the study and give them a brief overview. On the day of surgery, the consent for the study will be obtained after a pre-operative assessment and prior to initiating the regional block by the RAAPM team.

Single Injection interscalene brachial plexus nerve block with adjuvants vs. Liposomal bupivacaine interscalene brachial plexus nerve block for total shoulder arthroplasty

[figure not shown]
The study coordinator will then assign the patients will receive a study number, and the patient will be randomized by computer software algorithm to one of the study arms:

1. ISB using liposomal bupivacaine
2. ISB using plain bupivacaine with adjuvants

The study will be double blinded to patients, the perioperative nurses, the surgeon, and the study coordinators contacting the patient post-surgery.

To monitor our primary outcomes, patients will be asked to rate their pain level on a visual analog scale (Table 2, Appendix D) upon discharge from the PACU. Following discharge, they will continue to get every 12-hour pain assessments performed by research staff in person and/or over the phone (if they are discharged) until 48 hours have passed.

Table 2: Visual Analog Scale

Additionally, upon discharge, patients will be given a sheet to record the amount of narcotics and the time that they were used (Appendix G). At the 48-hour mark, patient's will be asked to rate their satisfaction with the procedure, and their willingness to recommend it, via Likert scale (Appendix E).

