5.4 Duration of Follow Up

Single Injection interscalene brachial plexus nerve block with adjuvants vs. Liposomal bupivacaine interscalene brachial plexus nerve block for total shoulder arthroplasty

Patients will be followed by research personnel upon arrival to the PACU, again 6 hours postoperatively, and then at 12, 24, 36 and 48 hours after surgery both in the hospital and at home via phone call.

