6.1 Analysis of Primary Objective

6.1.1 The VAS-NRS scale is an 11-point scale that assesses pain from 0- “No pain” to 10- “Worst possible pain”. For this study, a difference of ≥ 2 points will be considered to be clinically significant. Pain scores will be taken measured on departure from the PACU and at each 12-hour interval, and average pain scores for each cohort will be calculated. The area under the curve (AUC) for each cohort will be calculated using the least squares method. The inferiority threshold will be set as ≥ 2 points over 48 hours, which would result in an AUC difference of 96 point-hours.

Prior studies have found an AUC48 for ISB using liposomal bupivacaine to be 136.4 with a standard error of 12.09.¹⁰ There are no data evaluating the AUC48 for ISB using plain bupivacaine with adjuvants; however we estimate that the

Single Injection interscalene brachial plexus nerve block with adjuvants vs. Liposomal bupivacaine interscalene brachial plexus nerve block for total shoulder arthroplasty

pain scores will be within 20% of that of liposomal bupivacaine, resulting in an AUC48 of 163.0 or below, and a similar standard error of 12.09.

With a 2-sample t test using $\alpha = 0.05$ and $\beta = 0.1$, the study will be powered to detect a difference of 96 point-hours between the 2 groups with 36 subjects per arm.

To test for differences in these AUC between the 2 arms, an independent t-test will be used; if the observed p-value is <0.05 , statistical significance will be assumed. Two-sided t-test will be performed for statistical analysis once data collection is complete.

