Appendix H- Data Collection Form

| | |
|--------------|-----------------------------------------|
| | Assigned Study Number: |
| | WakeOne MRN |
| Demographics | Age |
| | Sex |
| Procedure | Comorbidities |
| | Pre-surgical analgesics |
| Medical Hx | Preop pain score |
| | Pre-op multimodal analgesics |
| | Post-Block assessment |
| Pre-Op | Intra-op Narcotics (PO oxy equivalents) |
| | Pain score in PACU p/t discharge |
| Intraop | PACU block assessment |
| | PACU opioids (PO oxy equivalents) |
| | +6hr worst pain score (VAS) |
| PACU | |
| | |

Single Injection interscalene brachial plexus nerve block with adjuvants vs. Liposomal bupivacaine interscalene brachial plexus nerve block for total shoulder arthroplasty

| | |
|------------------|-----------------------------------------------------------------------------------------------------------------------------------------------------------------------------------------------------------------------------------------------------------------------------------------------------------------------------------------------------------------------------------------------------------------------------------------------------------------------------------------------------------------|
| | 
+12h worst pain score (VAS)
 
+24h worst pain score (VAS)
 
+36h worst pain score (VAS)
 
+48h worst pain score (VAS)
 
+6hr opioid use (PO oxy eq)
 
+12h opioid use (PO oxy eq)
 
+24h opioid use (PO oxy eq)
 
+36h opioid use (PO oxy eq)
 
+48h opioid use (PO oxy eq)
 
Likert Satisfaction #1
 
Likert satisfaction #2 Nonopiod Analgesics Used Side effect evaluation (Itching, Nausea/vomiting)
 |
| Post OP | |
| Off study | 
("OFF" if applicable)
 
Reasons:
 |

Date of study completion:

Evaluable subject?

Protocol deviations?

Single Injection interscalene brachial plexus nerve block with adjuvants vs. Liposomal bupivacaine interscalene brachial plexus nerve block for total shoulder arthroplasty

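### The fixed 12-hour look-back in Appendix C does not fit the 6 h contact: used there as written, it can put pre-block shoulder pain into the score

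*Combined protocol and SAP*

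**What the plan says.** Appendix C, the Pain Assessment Form, carries one pain item: "Rate the intensity of your worst pain in the past 12 hours related to your operated shoulder". The look-back is fixed, with no variant for the PACU or for 6 h. Appendix C is the only form whose recall wording can be read. Appendix D is an image that is not shown.

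A 6 h score is scheduled in four places. Section 4.1.1 states "Pain levels (with shoulder movement) will be measured upon arrival to the PACU, at 6 hours, 12 hours" and continues to 48 h. Section 5.4 has research staff follow patients "upon arrival to the PACU, again 6 hours postoperatively, and then at 12, 24, 36 and 48 hours after surgery". Table 1 marks a pain score at 6 h. Appendix H has a field reading, in part, "6hr worst pain score (VAS"; its 12, 24, 36 and 48 h fields are also labelled as worst pain, but its PACU field is not.

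Two other places leave 6 h out. Section 6.1.1 says "Pain scores will be taken measured on departure from the PACU and at each 12-hour interval", and section 5.1 says that after the PACU "they will continue to get every 12-hour pain assessments performed by research staff".

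Table 1 also lists a "Pre-operative pain score" and places the block in the pre-operative column.

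**The concern.** A 12-hour recall fits contacts that are 12 hours apart. At 6 h it reaches back past the end of surgery, through the operation and possibly to the time before the block. The item asks for the worst pain in the operated shoulder, and that shoulder may have hurt before surgery. If the block works, the worst value in the window may be the pre-block one. The score would then reflect the condition being operated on, not the block.

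Section 4.1.1 puts the 6 h score into the primary AUC. Randomisation gives both arms the same expected distribution of pre-block pain. Replacing each patient's post-operative value by the larger of that value and a pre-block value pulls the two arm means together at 6 h. In a trial whose stated purpose is non-inferiority, shrinkage of a true disadvantage works in favour of the desired conclusion.

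**Working it through.** **The plan's own yardstick.** Section 6.1.1 sets the threshold at 2 points over 48 h: 2 × 48 = 96 point-hours. This reproduces.

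**Look-back windows.** With time 0 at the end of surgery, the window at time t is [t − 12, t].

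| Contact | Window (h) | Hours before end of surgery |
|---|---|---|
| 6 h | −6 to 6 | 6 of 12 |
| 12 h | 0 to 12 | 0 |
| 24 h | 12 to 24 | 0 |
| 36 h | 24 to 36 | 0 |
| 48 h | 36 to 48 | 0 |

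Asked an hour early (5 h), the first window reaches back 7 h; asked an hour late (7 h), 5 h. The 6 h and 12 h windows overlap over 0 to 6 h.

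**Pre-block time in the 6 h window.** This is 6 − (duration of surgery) − (block to incision), with a floor of 0. The documents give neither duration. Assuming 1 to 4 h of surgery and 0.5 to 2 h from block to incision, the result runs from 6 − 1 − 0.5 = 4.5 h to 6 − 4 − 2 = 0 h. In the grid examined (1, 2, 3, 4 h by 0.5, 1, 2 h) it is above zero in every combination except 4 h with 2 h.

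**Weight of the 6 h score.** The plan says only that the AUC uses least squares, so trapezoid weights are an assumption. On 0, 6, 12, 24, 36 and 48 h the weights are 3, 6, 9, 12, 12 and 6 h (sum 48). The 6 h score carries 6/48 = 12.5%. A peak in the first six hours that is reported at both 6 h and 12 h carries (6 + 9)/48 = 31.25%. On the section 6.1.1 schedule the 6 h score carries 0%.

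**Simple bound.** A 2-point difference at 6 h that is wholly hidden removes 2 × 6 = 12 point-hours, or 12/96 = 12.5% of the margin.

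**Attenuation by simulation.** The recorded 6 h score is max(pre-block pain, post-operative pain), on a rounded 0 to 10 scale, with the two values independent and 400,000 patients per arm. The adjuvant arm is taken to be the worse one. AUC loss = 6 × (true difference − recorded difference). No pain level below comes from the documents; means and SDs are before clipping to the scale, and pre-block SD is 2.

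*Set A: post-operative mean 1 (SD 1.5) against 3 (SD 2).*

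| Pre-block mean | True difference | Recorded | AUC loss |
|---|---|---|---|
| 3 | 1.84 | 0.82 | 6.1 |
| 4 | 1.84 | 0.56 | 7.7 |
| 5 | 1.84 | 0.34 | 9.0 |
| 6 | 1.84 | 0.19 | 9.9 |

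*Set B: post-operative mean 1 against 2 or 3 (SD 2 in both arms).*

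| Pre-block mean | True difference | Recorded | AUC loss |
|---|---|---|---|
| 2 | 0.77 | 0.42 | 2.1 |
| 2 | 1.67 | 0.97 | 4.2 |
| 4 | 0.77 | 0.18 | 3.5 |
| 4 | 1.67 | 0.49 | 7.1 |
| 6 | 0.77 | 0.06 | 4.3 |
| 6 | 1.67 | 0.17 | 9.0 |

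Across both sets the loss is about 2 to 10 point-hours: 2.1/96 = 2% to 9.9/96 = 10% of the margin. In set A the AUC rises in both arms, by 12.5 to 28.7 point-hours in the better arm and 6.4 to 18.8 in the other, so much of the inflation cancels in the comparison.

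**The case against.** The strongest reply is that nothing says Appendix C is used at 6 h. Section 5.1 names Appendix D as the scale for the primary outcome, no body section cites Appendix C, Table 1 refers to a pain diary, and the Appendix H field states no look-back. The 12-hour recall matches the 12-hourly contacts of sections 5.1 and 6.1.1, neither of which has a 6 h score. Section 4.1.1, read alone, asks for pain with movement at the time point, which has no look-back and so no contamination. All of this stands, and it makes the point conditional. It does not remove it: Appendix H labels the 6 h value as worst pain, and Appendix C is the only other place where worst pain is asked for.

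Four stronger readings are tempting, and the documents do not support them.

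- A reader might infer that Appendix C is the sole source of pain scores. Appendix D and the diary prevent that conclusion, and the PACU field in Appendix H does not ask for worst pain.
- A reader might infer that the error necessarily favours non-inferiority. It does so only if the adjuvant arm is worse at 6 h. If the arms are equal there nothing is lost; if the adjuvant arm is better, the shrinkage works against it. The documents give no 6 h data, and under section 5.2 both arms receive some plain bupivacaine.
- A reader might set the inflation of one arm's AUC against the predicted arm difference (163.0 − 136.4 = 26.6). That misleads, because both arms inflate.
- A reader might conclude that the trial's AUC cannot be compared with the planning value of 136.4. The documents do not say how the cited study asked about pain.

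**Conclusion.** The point holds in a conditional and modest form. If Appendix C is used at 6 h as worded, about half of its window precedes the end of surgery and the score can record pre-block pain. If section 4.1.1's schedule also governs the analysis, one-eighth of AUC48 is exposed, and a true 6 h difference can be attenuated by roughly 2 to 10 of 96 point-hours.

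That size rests on trapezoid weights, on assumed pain levels, on independence of pre-block and post-operative pain, and on patients using the full recall window literally. It would be zero if the 6 h score is left out of the AUC, or if pain with movement at the time point is what is recorded. The window mismatch itself needs none of the pain-level assumptions. It should be corrected because the correction is so cheap; it is not by itself a threat to the primary conclusion.

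**What to change.** First decide which measure is intended.

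- If worst pain is kept: in Appendix C, ask for the worst pain *since your surgery ended* at 6 h and *since your last pain rating* at 12, 24, 36 and 48 h. Label the Appendix H fields 0–6, 6–12, 12–24, 24–36 and 36–48 h. No window then starts before the end of surgery, and none overlap.
- If pain with movement at the time point is intended, as in section 4.1.1: remove the look-back from Appendix C and the word *worst* from Appendix H.

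In either case, align sections 4.1.1, 5.1 and 6.1.1 and Appendices C, D and H on one construct and one schedule, and state whether the 6 h score enters the AUC. Table 1 and section 5.4 should match that schedule.

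The cost is a wording change on one form, matching field labels and consistent cross-references. The one small downside is that 6 h scores already collected with the present wording need a flag and a sensitivity AUC that leaves them out.

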Appendix D- Verbal Numerical Rating Scale

https://www.physio-pedia.com/images/4/47/NRS_pain.jpg

Single Injection interscalene brachial plexus nerve block with adjuvants vs. Liposomal bupivacaine
interscalene brachial plexus nerve block for total shoulder arthroplasty

Appendix E – Satisfaction Questionnaire

Subject Number: _____ DATE: ____ / ____ / ____ TIME: ____ : ____ AM/PM

Instructions: On the second day (48 hours) after surgery, please review the following questions, and choose the answer that best corresponds to each question regarding your experience.

| | Strongly Disagree | Disagree | Neutral | Agree | Strongly Agree |
|--------------------------------------------------------------------|----------------------|----------|---------|-------|-------------------|
| I believe my pain was well-controlled during after surgery. | | | | | |
| I would recommend this pain-control treatment to another patient. | | | | | |
| Have you had any itching since your surgery in your shoulder area? | YES | NO | | | |
| Have you had any nausea and/or vomiting since your surgery? | YES | NO | | | |

Single Injection interscalene brachial plexus nerve block with adjuvants vs. Liposomal bupivacaine
interscalene brachial plexus nerve block for total shoulder arthroplasty

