- (C) An aggregate analysis of specific events observed in a clinical trial (such as known consequences of the underlying disease or condition under investigation or other events that commonly occur in the study population independent of drug therapy) that indicates those events occur more frequently in the drug treatment group than in a concurrent or historical control group.

In case a cardiac or neurological AE of special interest (AESI) or serious AE (SAE) occurs during the study, if the investigator considers that the event may be related to study treatment or suggests the possible occurrence of local anesthetic systemic toxicity (LAST; with or without the need for treatment [e.g., intralipids]), or if a plausible etiology for the event cannot be found, vital signs, and clinical laboratory tests will be performed per institutional standard of care of such occurrence. Cardiac AESIs include chest pain, abnormal/irregular heart rate, and shortness of breath requiring intervention.

Single Injection interscalene brachial plexus nerve block with adjuvants vs. Liposomal bupivacaine interscalene brachial plexus nerve block for total shoulder arthroplasty

Neurologic AESIs include seizure, altered mental status/ altered sensorium, tinnitus, visual disturbance, and severe dizziness.

This study involves a single administration of the study drug for the analgesic block; therefore, subjects should not be withdrawn from the ongoing study assessments as long as they are willing and able to continue with the follow-up schedule according to the protocol in order to obtain analgesic and safety data. Any subject exhibiting undesirable AESIs will receive appropriate treatment at the discretion of the investigator.

Subjects will be monitored for the occurrence of all potential adverse events by research personnel. This clinical research study will be paused after one death where a clear alternate cause is not readily apparent. The study will be paused after 2 non-fatal SAEs where a clear alternate cause is not readily apparent; the study will be paused after 3 moderate or severe adverse events of special interest. The adverse event(s) will be assessed by all investigators for causality and relationship prior to the study enrollment being resumed. Assessment of adverse event severity will be assessed and graded as per the definitions noted in Appendix I.

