APPENDIX I: ADVERSE EVENT GRADING SCALES

| LOCAL REACTION TO INJECTABLE PRODUCT | Mild (Grade 1) | Moderate (Grade 2) | Severe (Grade 3) | Potential life threatening (Grade 4) |
|--------------------------------------|----------------------------------------------------------|----------------------------------------------------------------------------------|--------------------------------------------------------------|--------------------------------------------------------|
| Pain | Does not interfere with activity | Repeated use of non-narcotic pain reliever >24 hours or interferes with activity | Any use of narcotic pain reliever or prevents daily activity | Emergency room visit or hospitalization |
| Tenderness | Mild discomfort to touch | Discomfort with movement | Significant discomfort at rest | Emergency room visit or hospitalization |
| Erythema/Redness | 2.5-5 cm | 5.1-10 cm | >10 cm | Necrosis or exfoliative dermatitis |
| Induration/Swelling | 2.5-5 cm and does not interfere with activity | 5.1-10 cm or interferes with activity | >10 cm or prevents daily activity | necrosis |
| <hr/> | | | | |
| VITAL SIGNS | Mild (Grade 1) | Moderate (Grade 2) | Severe (Grade 3) | Potentially Life threatening (Grade 4) |
| Fever-*F | 100.4-101.1 | 101.2-102.0 | 102.1-104 | >104 |
| Tachycardia | 101-115 | 116-130 | >130 | ER visit or hospitalization for arrhythmia |
| Bradycardia | 50-54 | 45-49 | <45 | ER visit or hospitalization for arrhythmia |
| Hypertension-systolic | 141-150 | 151-155 | >155 | ER visit or hospitalization for malignant hypertension |
| Hypertension-diastolic | 91-95 | 96-100 | >100 | ER visit or hospitalization for malignant hypertension |
| Hypotension | 85-89 | 80-84 | <80 | ER visit or hospitalization for hypotensive shock |
| Respiratory rate | 17-20 | 21-25 | >25 | Intubation |
| <hr/> | | | | |
| SYSTEMIC (GENERAL) | Mild (Grade 1) | Moderate (Grade 2) | Severe (Grade 3) | Potentially Life threatening (Grade 4) |
| Nausea/vomiting | No interference with activity or 1 – 2 episodes/24 hours | Some interference with activity or > 2 episodes/24 hours | Prevents daily activity, requires outpatient IV hydration | ER visit or hospitalization for hypotensive shock |
| Diarrhea | 2 – 3 loose stools | 4 – 5 stools | 6 or more watery stools or requires IV hydration | ER visit or hospitalization |

Single Injection interscalene brachial plexus nerve block with adjuvants vs. Liposomal bupivacaine

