interscalene brachial plexus nerve block for total shoulder arthroplasty

| | | | | |
|------------------------------------------------------------------------------------|-------------------------------|-----------------------------------------------------------------------------------------|---------------------------------------------------------------------------|-----------------------------|
| Headache | No interference with activity | Repeated use of nonnarcotic pain reliever > 24 hours or some interference with activity | Significant; any use of narcotic pain reliever or prevents daily activity | ER visit or hospitalization |
| Fatigue | No interference with activity | Some interference with activity | Significant; prevents daily activity | ER visit or hospitalization |
| Myalgia | No interference with activity | Some interference with activity | Significant; prevents daily activity | ER visit or hospitalization |
| Illness or clinical adverse event (as defined according to applicable regulations) | No interference with activity | Some interference with activity not requiring medical intervention | Prevents daily activity and requires medical intervention | ER visit or hospitalization |

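### The two side-effect questions in Appendix E ask about itching only at the shoulder and collect no severity, so they fall short of the Appendix H entry and the Appendix I grading that section 7.0 requires

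*Combined protocol and SAP*

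**What the plan says.** Appendix E, the satisfaction questionnaire completed at 48 hours, ends with two YES/NO items: "Have you had any itching since your surgery in your shoulder area" and "Have you had any nausea and/or vomiting since your surgery". No other side-effect question is worded anywhere in the protocol.

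Appendix H, the data collection form, has one matching entry, "Side effect evaluation (Itching, Nausea/vomiting". It names no body site and no grade.

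On severity, section 7.0 states: "Assessment of adverse event severity will be assessed and graded as per the definitions noted in Appendix I". Appendix I has a four-grade row for nausea/vomiting; its Grade 2 cell, for example, reads "Some interference with activity or > 2 episodes/24 hours". Itching has no row of its own, so the generic row, "Illness or clinical adverse event (as defined according to applicable regulations", would have to serve.

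Three other routes to adverse event data are named. Table 1 in section 5.0 marks "Review of potential adverse events" at 48 hours, when a coordinator call is also scheduled. Section 7.0 says "Subjects will be monitored for the occurrence of all potential adverse events by research personnel". Section 5.5 asks patients to report events themselves after discharge. Section 6.6 plans an interim analysis once each group has at least 10 patients, with evidence of severe side effects as its stated purpose.

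**The concern.** The forms do not fit together in two ways. The itching question is narrower than the entry it feeds, so the data set can show no itching for a patient who had it elsewhere. Neither question gathers what is needed to grade the event, although the protocol requires grading and wants an interim look at severe side effects.

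What is at stake is the tolerability half of the trial's question. Section 1.0 asks whether plain bupivacaine with inexpensive adjuvants can stand in for liposomal bupivacaine, and section 4.2.3 places evaluation of adverse events among the secondary outcomes. Under section 5.2 only the adjuvant arm receives buprenorphine in the block. An incomplete, ungraded side-effect record weakens what the trial can say about that mixture. Details not asked for at 48 hours are hard to recover later.

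**Working it through.** The plan gives no side-effect rate, so there is no figure of its own to reproduce. The check sets the forms side by side.

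**Step 1: does Appendix E feed Appendix H?** The last post-operative entries in Appendix H are Likert item 1, Likert item 2, non-opioid analgesics, then itching and nausea/vomiting. Leaving out the analgesics entry, this is the order of the four Appendix E items. No other form shown asks about itching or nausea. Appendix E is evidently the source, although no sentence says so.

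**Step 2: itching, question against entry.**
- Itching at the shoulder: the answer is YES and the entry is correct.
- Itching only elsewhere: the truthful answer is NO, and the entry reads as no itching.
- No itching: the answer is NO and the entry is correct.

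The second case is misrecorded.

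**Step 3: effect on a comparison of arms.** Let p be the proportion in an arm who itch anywhere and s the share of those who itch at the shoulder (between 0 and 1). If patients answer literally, the form records p × s. The recorded difference between arms A and B is p_A·s_A − p_B·s_B. If s is the same in both arms, this equals s × (p_A − p_B): the difference shrinks by the factor s, and the ratio of the two rates does not change. If s differs between arms, the recorded difference can be smaller or larger than the true one, or reversed. The documents give neither p nor s, so neither size nor direction can be derived.

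**Step 4: nausea/vomiting, question against grade.** Paraphrasing the Appendix I row:

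| Grade | What must be known | Asked in Appendix E? |
|---|---|---|
| 1 | activity unaffected, or one or two episodes a day | no |
| 2 | activity partly affected, or more than two episodes a day | no |
| 3 | daily activity prevented, outpatient IV fluids needed | no |
| 4 | emergency or hospital care for hypotensive shock | no |

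A YES is compatible with all four grades, so none can be assigned from it.

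**Step 5: itching, question against grade.** The generic row turns on interference with activity, need for medical intervention, and emergency or hospital care. Appendix E asks none of these, so a YES on itching cannot be graded either.

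**Step 6: is the grade stored elsewhere?** Appendices B, C, F, G and H have no severity grade field. Appendix F mentions submitting an event on a case report form, but only in connection with withdrawal, and that form is not among the documents.

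**The case against.** The strongest reply is that a satisfaction questionnaire was never meant to be the grading instrument. Staff can review events at the 48-hour call, the investigator follows up reported events and judges causality and outcome, and a YES can prompt questions about site and severity. A case report form whose content is not shown may hold the grade.

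Much of this stands: the protocol does not rely on Appendix E alone. It does not close the gap. None of these routes has a question set or a grade field in the documents, so what is collected depends on the caller. In Table 1 the 48-hour review shares its row and time point with the satisfaction assessment, which is what Appendix E collects. A NO from a patient who itches elsewhere prompts no follow-up.

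Three stronger readings are tempting but unsupported.
- A reader might infer that the adjuvant arm is made to look better tolerated. Both arms may receive fentanyl, hydromorphone or oxycodone for breakthrough pain (section 5.3), so opioid exposure is not confined to one arm, and step 3 leaves the direction open.
- A reader might infer that a planned test is spoiled. Section 6 specifies no between-arm test of side effects; section 6.2.3 covers only satisfaction and recommendation.
- A reader might object to combining nausea with vomiting. Appendices H and I combine them too, so the item is consistent on that point; what is missing is severity.

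**Conclusion.** The point holds as a mismatch between forms. The itching item does give a record, but only for the shoulder area, and itching elsewhere is lost unless another route happens to catch it. Neither item yields the grade that section 7.0 calls for, and these items cannot by themselves serve the interim analysis's stated purpose of detecting severe side effects.

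A reader might also infer that the pausing rule in section 7.0 is disabled. It is not: its grade-dependent trigger concerns moderate or severe adverse events of special interest, and neither itching nor nausea/vomiting is on those lists.

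No number can be put on the loss, because the documents give no rates and no share of itching at the shoulder. The conclusion rests on two assumptions: that patients answer the itching question literally, and that Appendix E supplies the Appendix H entry. The primary outcome, sample size, power and alpha are unaffected. The change is worth making because it is cheap and improves the safety data.

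**What to change.** In Appendix E, delete the restriction to the shoulder area, or ask about the shoulder and elsewhere as two items. After a YES to either side effect, add follow-up items with criteria copied verbatim from Appendix I: the nausea/vomiting row for that item, and the generic clinical adverse event row for itching. Copy the cells as they stand, including the qualifiers in Grades 3 and 4, so that the answers map directly to a grade.

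In Appendix H, add a grade field for each of the two side effects. In section 6, state that incidence and grade will be reported by arm descriptively, and that the interim look in section 6.6 will use them.

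The cost is revised form wording, two data fields and about a minute more at the 48-hour contact. If enrolment has begun, answers already collected stay on the old wording and should be tabulated separately.
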